A side effect of dantrolene is mild muscular weakness^{40,41}. The impact of dantrolene, specifically Ryanodex, on respiratory mechanics, however, is unclear. Dantrolene is typically given to patients with malignant hyperthermia who are intubated, who have been given neuromuscular blocking drugs, and who are under general anesthesia, since the triggers for malignant hyperthermia require general anesthesia or paralytic administration. We seek to measure the effect of the administration of dantrolene/Ryanodex on incidence of interventions to support respiration (bag/mask ventilation, CPAP, BiPAP, LMA placement, tracheal intubation) in the perioperative period. We will also compare additional markers of respiratory mechanics and strength (secondary endpoints) between groups including negative inspiratory force, dynamometer measured grip strength, accelerometer measured twitch strength and train-of-four, ventilation (respiratory rate, tidal volume, minute ventilation), markers of gas exchange (arterial pH, pCO₂, pO₂, base excess), and electrolytes.

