Research by our group and others has focused on the role of diastolic calcium (Ca) leak via the RyR2 channel as a cause of delayed afterdepolarizations (DADs) and polymorphic VT in rare genetic disorders such as catecholaminergic polymorphic VT (CPVT).^{44,45} This led to the discovery that drugs which stabilize the RyR2 channel eliminate DADs and polymorphic VT in CPVT; this includes not only the experimental probe drug ent-verticilide but also clinically used agents such as flecainide and its derivatives and dantrolene, which is being studied here.^{46,47} The recognition that structural heart disease results in post-translational modification of RyR2 and diastolic Ca leak is consistent with the idea that Ca leak is also involved in generating VT/VF in more common diseases.⁴⁸⁻⁵¹ Accordingly, the **overarching hypothesis** to be tested is that RyR2 hyperactivity in patients with structural heart disease drives proarrhythmic changes in refractoriness and conduction, and decreases cardiac contractility, which promotes VT/VF (**Figure 1**).

Despite the success of flecainide to treat CPVT, it is relatively contraindicated in patients with structural heart disease because of its Na-channel inhibition. Dantrolene, a currently available drug that inhibits RyR2, but has no Na or K channel activity, will be used as a tool to study RyR2 modulation. Here, we propose a randomized controlled trial of dantrolene versus placebo in patients with structural heart disease referred for VT ablation to evaluate electrophysiologic, hemodynamic, and arrhythmia prevention endpoints. Dantrolene's inhibition of RyR1 will also be studied to define its effect on muscle and respiratory strength in this clinical population, which will be important if dantrolene is to be considered for repurposing as an antiarrhythmic drug. Accordingly, we propose the following Specific Aims:

Aim 1: To conduct a randomized, placebo-controlled trial of dantrolene to study the effect of RyR inhibition on cardiac electrophysiology, hemodynamics, arrhythmia inducibility, muscle strength, and respiratory mechanics in patients with structural heart disease referred for VT ablation.

Aim 2: To explore the pharmacokinetic/pharmacodynamic relationship of I.V. dantrolene and its short-term effect on cardiac electrophysiology, hemodynamics, and muscle and respiratory strength.

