Least inducible	0	No sustained VT/VF or NSVT
	1	1 episodes of NSVT with S4
↓	2	1 episodes of NSVT with S3
↓	3	1 episodes of NSVT with S2
↓	4	2 episodes of NSVT with S4*
↓	5	2 episodes of NSVT with S3*
↓	6	2 episodes of NSVT with S2*
↓	7	Sustained VT/VF with S4
Most inducible	8	Sustained VT/VF with S3
	9	Sustained VT/VF with S2

*the category assigned for 2 episodes of NSVT is based on the extrastimulus used to induce the second episode of NSVT.

Table 6. Secondary analysis of rhythm stability

	Category	
Least Stable	1	Ventricular Fibrillation
	2	Polymorphic VT
↓	3	Pleomorphic VT
↓	4	Unstable Monomorphic VT
Most Stable	5	Stable Monomorphic VT
	6	No Inducible VT/VF

safety concerns, and no adverse events have been observed, we planned the assessment of safety, which will be based on the frequency of adverse events. Other safety data such as blood pressure will be considered. All adverse events recorded during the study will be summarized. See Ethical Aspects of the Proposed Research for DSMB.

Respiratory Mechanics and Ventilation Endpoints: To monitor adequacy of ventilation, maintain safety, and measure the effect of dantrolene administration on ventilation, the anesthesiologist will monitor respiration and oxygenation as is standard of care for all patients during procedures and surgeries. The primary endpoint of the Respiratory Mechanics substudy is the incidence of the addition of respiratory support, including bag/mask ventilation, CPAP, BiPAP, LMA, or tracheal intubation, from the time of study drug administration until 120 minutes after study drug administration. Placement of airway support devices is at the discretion of the attending anesthesiologist and will be based on standard safety parameters such as oxygen saturation, adequacy of ventilation, and airway obstruction. Secondary endpoints include additional markers of respiratory mechanics and strength including negative inspiratory force, dynamometer measured grip strength, accelerometer (respiratory rate, tidal volume, minute ventilation), markers of gas exchange (arterial pH, pCO₂, pO₂, base excess), and electrolytes. Tidal volume, respiratory rate, and minute ventilation parameters will be continuously collected (recorded every minute) as available. We will summarize these data prior to study drug administration and at 10 and 20-minutes after dantrolene administration.

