Prior to the ablation procedure and administration of anesthesia, a baseline negative inspiratory force (NIF) will be collected x3 in the supine position. A repeat NIF measurement will be again collected in the PACU 2 hours post dantrolene administration and then again at 24 hours. We will summarize NIF data prior to and following dantrolene administration.

Arterial blood gas (ABG) sampling will be performed at four time points: intraoperatively just prior to dantrolene administration, 10- and 20-minutes post dantrolene administration, and 2 hours post dantrolene administration in the PACU. ABG sampling will allow sampling of respiratory mechanic parameters including pH, pCO₂, pO₂, and base deficit/excess. We will summarize ABG data at these four timepoints.

Muscle Strength Endpoints: We will assess grip strength as measured with a handheld dynamometer x3 prior to the ablation procedure and administration of anesthesia and 2 hours following dantrolene administration and then again at 24 hours. We will summarize these data.

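### NIF, grip, ventilation and blood gas analyses are written only as before/after summaries; the promised dantrolene-versus-placebo comparison, with baseline adjustment, still has to be specified

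*Combined protocol and SAP*

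**What the plan says.** Two parts of the combined protocol and SAP set a comparative objective. Section 1.6 states: "We will also compare additional markers of respiratory mechanics and strength (secondary endpoints) between groups including negative inspiratory force". Aim 1 in section 2.0 is a randomised, placebo-controlled trial to "study the effect of RyR inhibition on cardiac electrophysiology, hemodynamics, arrhythmia inducibility, muscle strength, and respiratory mechanics".

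The endpoint-specific text in section 10.0 is descriptive for all four groups of markers:

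- Ventilation: "We will summarize these data prior to study drug administration and at 10 and 20-minutes after dantrolene administration".
- NIF: "We will summarize NIF data prior to and following dantrolene administration".
- Blood gases: "We will summarize ABG data at these four timepoints".
- Grip: "We will summarize these data".

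None of these sentences names an arm contrast, a test, a model or a covariate.

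The General Statistical Strategies in section 10.0 give t-tests or ANOVA (or rank tests) between groups for single time points, and mixed-effect models for repeated measurements. They do not exclude these markers and do not say how a baseline value enters.

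By contrast, the same section adjusts conduction time, ERP, cardiac index and PA diastolic pressure explicitly for the pre-drug value.

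**The concern.** The objective is comparative and the stated analysis is descriptive. Sections 6.13 and 6.14 add to the before/after impression, because they present the repeat NIF and grip tests as a check on return to baseline.

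For NIF and grip the choice matters. The baseline is taken "Prior to the ablation procedure and administration of anesthesia", and the first repeat comes 2 hours after study drug. The ablation and its sedation (typically propofol and dexmedetomidine, section 6.1) lie in between. A fall from baseline within the dantrolene arm could therefore come from the drug, from sedation or from the procedure. Section 2.0 says the effect on muscle and respiratory strength will be important if dantrolene is considered for repurposing, so this attribution is what the measurements are for.

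Precision is also at stake. Only 28 patients receive placebo, and the baseline is collected but given no stated role in the analysis.

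**Working it through.** The documents give no effect size, SD, correlation or power for these markers, so there is no stated figure to reproduce. The sizes below use the planned 56 dantrolene and 28 placebo patients, a two-sided 5% level, and assumed values for the correlation r between baseline and follow-up and for a common non-drug shift.

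**1. Where each baseline sits (sections 6.1, 6.13, 10.0)**

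| Marker | Baseline in section 10.0 | Follow-up | Anaesthesia starts between the two? |
|---|---|---|---|
| NIF, grip | before procedure and anaesthesia | 2 h, 24 h | yes |
| Ventilation | before study drug, during the procedure | 10, 20 min | no |
| Blood gases | intraoperative, just before drug | 10, 20 min, 2 h | no |

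Section 6.6 says sedation is held constant through the study protocol, with changes documented. That supports the 10- and 20-minute comparisons. The 2-hour gas is taken in recovery, so sedation differs there too, but as recovery from sedation and not as its onset. Table 2 in section 6.1 also lists a NIF in the intraprocedural block before study drug, which sections 6.13 and 10.0 do not mention.

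**2. NIF or grip read within the dantrolene arm only, with no drug effect**

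In units of the marker's SD, the SD of the change is sqrt(2(1 − r)). The paired t-test has noncentrality (shift / sqrt(2(1 − r))) × sqrt(56). For a shift of 0.3 SD:

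- r = 0.5: 0.3 / 1.000 × 7.483 = 2.245, so p < 0.05 in 59.7% of trials.
- r = 0.7: 0.3 / 0.775 × 7.483 = 2.898, so p < 0.05 in 81.3% of trials.

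| Common shift (SD) | r = 0.5 | r = 0.7 |
|---|---|---|
| 0 | 5.0% | 5.0% |
| 0.1 | 11.4% | 15.8% |
| 0.2 | 31.3% | 47.6% |
| 0.3 | 59.7% | 81.3% |
| 0.5 | 95.7% | 99.7% |

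**3. The same data compared between arms**

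In 5,000 simulated trials with a 0.3 SD shift in both arms and no drug effect, the rejection rates were:

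- Post-only t-test: 4.5% (r = 0.5) and 4.7% (r = 0.7).
- ANCOVA: 4.8% and 5.3%.

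The arm contrast removes the common shift with or without baseline adjustment.

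**4. What baseline adjustment adds**

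The standard error ratio of ANCOVA to a post-only comparison is sqrt(1 − r²). The post-only comparison of 56 with 28 detects 0.656 SD at 80% power. Multiplying by the ratio gives, approximately:

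| r (assumed) | sqrt(1 − r²) | SE reduction | Detectable difference |
|---|---|---|---|
| 0.3 | 0.954 | 5% | 0.626 SD |
| 0.5 | 0.866 | 13% | 0.568 SD |
| 0.7 | 0.714 | 29% | 0.469 SD |
| 0.8 | 0.600 | 40% | 0.394 SD |

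**The case against.** The best defence is that the plan already contains the comparison. Section 1.6 promises it, and the general rules in section 10.0 supply the tools. NIF and grip (three time points) and gases (four) are repeated measurements, so the mixed-model rule arguably governs them and the unadjusted t-test does not. The protocol also uses dantrolene loosely to mean study drug. Section 6.5, for example, describes conduction restitution as compared before and after dantrolene, yet section 10.0 analyses it by treatment arm with adjustment for the pre-drug value. Before/after wording therefore does not prove a single-arm analysis. These are also secondary markers with no power claim.

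All of this stands, and it rules out several stronger readings:

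- A reader might infer that no between-arm comparison is planned, or that baseline adjustment has been given up. Both are left unspecified, not excluded.
- A reader might infer that the effect of anaesthesia will be reported as a drug effect. That happens only if the summaries are read within the dantrolene arm. The randomised placebo arm removes a common shift once the arms are compared.
- A reader might extend the pre-anaesthesia argument to gases and ventilation. Their baseline is intraoperative, so it does not apply at 10 and 20 minutes.
- A reader might quote a precision gain of 29% to 40%. That assumes correlations of 0.7 to 0.8 and a post-only t-test that the plan does not clearly prescribe.

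The defence does not supply a named contrast or a baseline term. Nor does it settle the analysis set. The safety set is defined by receipt of dantrolene, and the respiratory endpoints are assigned to no set, so inclusion of the placebo patients should be stated.

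**Conclusion.** The gap is real, but it is one of specification. For NIF, grip, ventilation and gases the endpoint text stops at a before/after summary, although the stated objective is "We will also compare additional markers of respiratory mechanics and strength (secondary endpoints) between groups". The general rules would permit that comparison without fixing its form.

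For NIF and grip, a within-arm reading would be uninterpretable as a drug effect. With no drug effect and an assumed common shift of 0.3 SD, it would be nominally significant in about 60% to 81% of trials (r = 0.5 to 0.7), against about 5% for either between-arm analysis. The documents give neither the shift nor the correlation, so these figures are illustrations and do not forecast what the trial will report.

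An unadjusted between-arm test would be valid. Adjustment buys precision only, from about 5% off the standard error at r = 0.3 to 40% at r = 0.8. The change is worth making because the baseline is already collected and the trial's main continuous endpoints already use theirs.

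**What to change.** In the respiratory mechanics and muscle strength paragraphs of section 10.0, replace the commitment to summarise with the following:

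- State that each marker is compared between dantrolene and placebo, and name an analysis set that includes the placebo patients.
- For NIF and grip at 2 and 24 hours, use ANCOVA at each time, or a mixed model with arm, time, arm-by-time, baseline value and the two randomisation strata from section 5.0 (amiodarone use, planned PVC versus VT ablation). Report the adjusted arm difference with a 95% confidence interval at each time.
- Use the same model for ventilation at 10 and 20 minutes and for blood gases at 10 and 20 minutes and 2 hours, with the intraoperative pre-drug value as baseline.
- Reconcile the NIF schedule between Table 2, section 6.13 and section 10.0, and state which measurement is the baseline in the model.
- Keep the before/after summaries as descriptive tables, by arm.

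The cost is SAP wording and a few extra models, with no new data. The text should be fixed before unblinding, so that the choice of model and baseline cannot depend on the results.

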11.0 PRIVACY AND CONFIDENTIALITY ISSUES

All records are retained on password-protected computers accessible only to members of the study team. Computers containing these records are only connected to networks if they include appropriate firewalls and security measures. Deidentified records and DNA samples may be shared with other investigators who have IRB-approved protocols and who agree to comply with the protections provided at this institution. These research materials are transferred only by secure methods. The identity of any individuals and their families are not to be revealed in any publication without their written informed consent.

12.0 FOLLOW-UP AND RECORD RETENTION

The expected duration of this study is estimated to be 6 months. The study results will be retained for at least six years after the study is completed. At that time, the research information not already in the medical record will be destroyed.

